Appendix A Signatures

Appendix B ICD9 and ICD10 codes

LIST OF FIGURES

Figure 1 Patient flow

LIST OF ABBREVIATIONS AND DEFINITION OF TERMS

The following abbreviations and special terms are used in this NIS Protocol.

Abbreviation or special term	Explanation
APA	American Psychiatric Association
ATC	Anatomical Therapeutic Chemical classification system
AZ	AstraZeneca
BD	Bipolar Disorder
DBA	Data Base Audit
DDD	Defined Daily Dose
EC	Ethics Committee, synonymous to Institutional Review Board (IRB) and Independent Ethics Committee (IEC)
ICD	International Classification of Diseases
ICH	International Conference on Harmonisation
National Coordinator	The National Coordinator is the main line of contact to coordinate the submissions and responses of the Ethics Committee.
NPR	National Patient Register
NBHW	National Board of Health and Welfare
OTC	Over-the-counter drugs, medicines sold without a prescription
PDR	Prescribed Drug Register
PIN	Personal Identification Number
Quetiapine IR	Immediate Release quetiapine
Quetiapine XR	Extended Release quetiapine
SCB	Statistics Sweden
Variable	A characteristic of a property of a an item that may vary eg, from time to time between items

Data base Audit Study Protocol DBA Code VD-NS-1101 Edition Number 1.0

1. INTRODUCTION

1.1 Background

Psychiatric disorders account for a large part of the global burden of disease (Prince et al 2007). Bipolar disorder (BD) is a lifelong illness characterized by one or more episodes of mania or hypomania usually alternating with recurring major depressive episodes, which is an important contributor to this disease burden (Prince et al. 2007, APA 2002). The estimated lifetime prevalence of bipolar I and II disorder is affecting an estimated 0.5–5% of adults and characterized by a heterogeneous course, including: hypo manic, manic, or depressed episodes; slow or incomplete recovery from acute episodes; risk of recurrence; and sustained morbidity over time (Kupfer 2004, Pini 2005, Merikangas et al. 2007). BD cause substantial loss of function for many patients, and place high financial and social burdens on caregivers, the health care system and society as a whole. The economic implications of these disorders may have been previously underestimated (Grant et al. 2005).

BD is a progressive illness that requires long-term treatment. Individualizing drug treatments in BD is crucial for treatment success, with respect to side effects, adherence challenges and patient preferences (Altamura et al. 2008, Parks et al. 2009). Different patient and drug characteristics therefore determine the psychiatrist's drug choice. Adherence is a major problem and a range of treatment options are needed.

Immediate-release quetiapine (quetiapine IR) and extended-release quetiapine (quetiapine XR) are both indicated in Europe for the treatment of bipolar I and II disorder. The two formulations of quetiapine have different characteristics. Quetiapine XR is characterized by once-daily dosing, faster dose titration and different pharmacological profile with different occupancy on dopamine D2 receptors and has different tolerability profiles compared to quetiapine IR (Datto et al. 2009, Figueroa et al. 2009, Meulien et al. 2010, Peuskens et al. 2007, Nord et al. 2011). The differences between the two formulations of quetiapine may potentially result in differential use in clinical practice in BD.

Differential use of quetiapine IR and quetiapine XR has been documented in schizophrenia in Sweden and Finland. In Sweden, "A retrospective, naturalistic study evaluating the use of quetiapine XR and quetiapine IR in the clinical practice of inpatients in schizophrenia in Sweden" documented differences between the two quetiapine formulations in mean doses, number of add-on medications, disease severity and reasons for treatment in 178 inpatients with schizophrenia across 14 psychiatric clinics (Eriksson et al. 2011). A Finnish study (Hallinen et al. 2011, "the Lappeenranta study") documented a similar differential use of quetiapine XR and IR in 156 inpatients at the South Karelia Central Hospital in Lappeenranta. A small sample with BP mania was included in the in the Finnish study (The Lappeenranta study) and differential use was documented.

We aim to investigate the clinical practice treatment in BD in Sweden, with particular focus on the use of quetiapine XR and quetiapine IR.

1.2 Rationale for conducting this DBA

Quetiapine IR and quetiapine XR are both indicated in Europe for the treatment of BD. The target dose depends on if the episode is depression or mania. In treatment of bipolar depression the target dose is 300 mg and in the treatment of mania the target dose is 600-800 mg. In maintenance treatment the dosing is 300-800 mg with quetiapine XR and 300-750 mg with quetiapine IR, depending on if the patient needs protection for depression or protection for both depression and mania.

It has been shown differences between quetiapine XR and quetiapine IR in plasma concentration profile, occupancy in D2 receptors and tolerability profile according to sedation. Fast titration is an advantage in treatment with quetiapine XR. Results of two studies (Datto et al. 2009) and study code D1443C00040 (Reported 2010, data on file) supported a different tolerability profile in quetiapine XR and quetiapine IR, with different sedation profile. Nord et al. 2011 have shown different D2 occupancy profile for quetiapine XR and quetiapine IR.

Psychiatrists have discussed that, due to the different characteristics, quetiapine XR and quetiapine IR are used differently in the clinical practice of patients with BD. Quetiapine XR, is believed to be primarily used as foundation treatment, whilst quetiapine IR is believed to be more commonly used in lower doses as add-on to other treatments. In the treatment of schizophrenia two non-interventional (NIS) studies in Finland (Hallinen et al. 2011, "the Lappeenranta study") and in Sweden (Eriksson et al. 2011) have shown differential use with quetiapine XR and quetiapine IR. Many patients were treated with higher doses of quetiapine XR compared to when treated with quetiapine IR and patients were frequently treated with both formulations at the same time. In Lappeenranta, only few patients with BD mania were investigated.

The aim of this study is to describe the treatment pattern and describe patient characteristics in real life setting in patients with BD treated with quetiapine XR and/or quetiapine IR in Sweden. No outcome analysis will be performed between the formulations due to the high amount of confounding factors.

The clinical everyday use of quetiapine XR and quetiapine IR, when treating patients with BD, is unknown and explorative assessment of patient and drug treatment characteristics will be performed.

2. DBA OBJECTIVES

2.1 Primary objective

The primary objective of the study is to describe the detailed clinical treatment (including duration of treatment, doses, drug switches, and add-on therapy), in patients with BD and on treatment with quetiapine XR and/or quetiapine IR before, at and after the index date.

2.2 Secondary objectives

- 1. To describe co-morbidity, demographics, sick leave, early retirement and socioeconomic factors in patients with BD and on treatment with quetiapine XR and/or quetiapine IR before and at the index date.
- 2. To describe the detailed clinical treatment (including duration of treatment, doses, drug switches, and add-on therapy) in patients with BD, including all drug treatment after the index date.
- 3. To describe co-morbidity, demographics, sick leave, early retirement and socioeconomic factors in patients with BD, including all drug treatment before and at the index date

3. STUDY PLAN AND PROCEDURES

This DBA Study Protocol has been subject to an internal review according to AstraZeneca standard procedures.

[figure not shown]
3.1 Study Design

This is an epidemiological registry study on all patients who have been hospitalised in Sweden at least once since 1987 with a diagnosis during hospitalisation of BD and/or schizophrenia spectrum disorder. Index visit (baseline) is defined as the date when a patient dispensed their first prescription of quetiapine XR and/or quetiapine IR. Patients with index visit between 1st of January 2009 and 31st of December 2010 will be more detailed described, and data will be collected six months prior to the first dispensed prescription of quetiapine XR and/or quetiapine IR. Patients started their treatment with quetiapine XR and/or quetiapine IR before 1st of January 2009 will have 1st of January 2009 as index visit.

May 2008 quetiapine XR was launched for the indications schizophrenia and bipolar mania in Sweden and March 2009 quetiapine XR and IR was launched in bipolar depression.

Data on patients with schizophrenia spectrum disorder will be collected in order to allow us to exclude patients who have been re-diagnosed to or from bipolar disorder. The latest diagnose is defined as the patients diagnose, i.e. if a patient gets a schizophrenia spectrum disorder diagnose after diagnose of bipolar disorder, the patient will not be included in the study.

Figure 1 Patient flow

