3.3.2 Prescription Drug Register

The Prescribed Drug Register was started July 1, 2005 and is updated each month. The register comprises national coverage of dispensed drugs, pharmacies (dispensed drugs), not including OTC and in-patient care.

The variables include the patient's ID-number (PIN) and place of residence. Also registered is information about dispensed drugs (by ATC code), dates, dosages and for an unknown proportion indication in free text, DDDs, and expenditure. Information on the prescriber's profession (physician or other) and specialist code are registered.

PDR can be linked to other national registers by the unique patients PIN. Limitations include the lack of in-patient drug use and the lack of specific coding of the indication and prescribed dose. Information on indication and prescribed dose may in many cases be retrievable by text search procedures.

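### Pre-2009 starters get a fixed index date of 1 January 2009 and are not separated from 2009–2010 starters, so treatment duration is cut off, potentially by far more for IR than for XR

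*Protocol*

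**What the plan says.** Protocol section 3.1 gives a general rule: "Index visit (baseline) is defined as the date when a patient dispensed their first prescription of quetiapine XR and/or quetiapine IR". It then gives a second rule: patients who began quetiapine XR and/or "quetiapine IR before 1st of January 2009 will have 1st of January 2009 as index visit". The same section says "Patients with index visit between 1st of January 2009 and 31st of December 2010 will be more detailed described", a window that includes the assigned date, and adds that "data will be collected six months prior to the first dispensed prescription of quetiapine XR and/or quetiapine IR".

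Other sections bear on the point:

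- Section 2.1 states the primary objective for treatment "in patients with BD and on treatment with quetiapine XR and/or quetiapine IR before, at and after the index date".
- Section 9.1 lists the treatment variables (duration, dose, switching, packages, co-medication) for the period after index. For the period before index it lists only the number and total length of hospital stays.
- Section 5.2 describes co-morbidities at an index visit that comes before quetiapine treatment.
- Sections 4.1 and 4.2 have one inclusion criterion (a bipolar diagnosis) and one exclusion criterion (a later schizophrenia spectrum diagnosis). Neither concerns current or recent quetiapine use.
- On timing, section 3.1 says "May 2008 quetiapine XR was launched for the indications schizophrenia and bipolar mania in Sweden" and section 3.3.2 says "The Prescribed Drug Register was started July 1, 2005".

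**The concern.** The two rules set different time zeros. For a 2009–2010 starter, index is the start of treatment. For anyone earlier, it is a calendar date at some point after the start. Duration measured from index is then complete from the beginning in one group and left-truncated in the other. Dose and co-medication at index are starting values in one group and values of established users in the other.

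This would matter less if it fell equally on both formulations, but it need not. XR had been on the market for at most 8 months at the fixed date, while IR use can be seen in the register for up to 42 months. Section 1.2 gives the expected difference in use between XR and IR as the reason for the study. Duration, dose, switching and add-on therapy, the content of the primary objective, can all vary with time since treatment began. A difference between formulations could therefore arise partly from who is a prevalent user and who is new.

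**Working it through.** The protocol gives no figure of its own to reproduce: the study is descriptive and section 9.2 has no formal sample size calculation. The check is calendar arithmetic on the protocol's dates (one month = 30.4375 days), followed by a comparison of sections.

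**1. Use that can fall before the fixed index date of 1 January 2009**

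- Register-visible IR: 1 July 2005 to 1 January 2009 = 1280 days; 1280/30.4375 = 42.1 months.
- XR, launch on 1 May 2008: 245 days; 245/30.4375 = 8.0 months.
- XR, launch on 31 May 2008: 215 days; 215/30.4375 = 7.1 months.
- Ratio of ceilings: 42/8 = 5.25, or 42/7 = 6.0.

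**2. Share of treatment time cut off**

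Assume continuous use followed to 31 December 2010, about 24 months after the fixed date.

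- IR: up to 42/(42 + 24) = 42/66 = 64%.
- XR: up to 8/(8 + 24) = 8/32 = 25%.

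For example, one patient starts IR on 1 July 2005 and another on 1 January 2009, and both continue to the end of 2010. Both have about 24 months of duration after index, but their treatment has lasted about 66 and 24 months.

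**3. Sensitivity to the missing IR launch date**

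The date of the earliest IR dispensing is an assumption here; the XR ceiling is held at 8 months.

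| Earliest IR dispensing (assumed) | Months before 1 January 2009 | Ratio to XR |
|---|---|---|
| July 2005 | 42.1 | 5.2 |
| July 2006 | 30.1 | 3.7 |
| July 2007 | 18.1 | 2.2 |
| January 2008 | 12.0 | 1.5 |

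**4. Look-back window**

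The six months run back from first dispensing, not from index. For a start on 1 March 2007 the window is 1 September 2006 to 1 March 2007, which ends 22 months before index. For any start before 1 July 2008 the window does not overlap the six months before index at all. For starts before 1 January 2006 it reaches back past the start of the dispensing register (1 January 2006 minus six months = 1 July 2005).

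**5. Sections side by side**

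- Section 2.1 wants treatment described before index; section 9.1 lists treatment variables only after it.
- Section 5.2 places index before treatment; under the second rule of section 3.1 index comes after treatment began. Both cannot hold for a pre-2009 starter.

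**6. Can the groups be separated?**

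Yes. A patient with a first dispensing between 1 January 2009 and 31 December 2010 has 42 to 66 months of earlier register time in which to confirm that there was no previous quetiapine.

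**The case against.** The strongest reply is that this is a descriptive study with no outcome comparison between formulations (section 1.2), that a fixed calendar baseline is a recognisable way to describe existing users, and that stratified tables belong in a SAP, which is not shown. Figure 1 on patient flow is also not visible. Part of this stands: no error rate is affected, and the two groups may be split somewhere out of sight. But the index rule and the list of variables are fixed in the protocol itself, and the measures affected are those of the primary objective.

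A reader might also infer more than the text supports:

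- *That stopped users enter with zero dose and duration.* Sections 3.1, 4.1 and 4.2 do not exclude a patient whose only dispensing was in 2006. However, sections 2.1 and 2.2 describe the quetiapine patients as on treatment at index, which suggests that former users are not meant to be counted. What is missing is an operational rule.
- *That the earlier history is lost.* The register holds it from July 2005, and collection from before the first dispensing may retrieve it. It is left out of the listed analysis.
- *That prevalent users are almost all IR.* No figure supports this. The index rule works at the level of quetiapine, so a patient on IR in 2007 who moved to XR in 2009 also gets 1 January 2009.
- *That 42 and 8 months are typical.* They are ceilings.
- *That the March 2009 launch in bipolar depression adds a separate bias between formulations.* It applied to both, and January–February 2009 starters also precede it.

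**Conclusion.** The concern holds in this form. The protocol uses two time zeros, states no separation between them, and lists treatment duration, dose and switching only after index. For pre-2009 starters, duration is left-truncated and values at index are those of established users. The cut can reach 42 months for IR (64% of treatment time for a continuous user followed to the end of 2010) against about 8 months for XR (25%). XR and IR descriptions would then partly reflect prevalent versus new use.

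The XR ceiling is firm. The IR ceiling assumes dispensing from the register's first day; the ratio falls from 5.2 to 1.5 if the earliest IR dispensing was in January 2008. The number of patients affected cannot be derived from the protocol. The mismatches over the look-back, co-morbidity timing and pre-index treatment are visible in the text and need none of these assumptions.

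**What to change.** 1. Report two strata and show XR and IR within each: new users (first dispensing in 2009–2010, none earlier in the Prescribed Drug Register since July 2005) and prevalent users at 1 January 2009.
2. For prevalent users, count duration from the actual first register dispensing. Flag it as left-truncated when that dispensing falls in the register's first months.
3. Assign index 1 January 2009 only to patients whose dispensed supply covers that date. Index those who had stopped at their first dispensing in 2009–2010, and label them restarters.
4. State the six-month look-back relative to index, reconcile section 9.1 with section 2.1 on treatment before index, and restrict the co-morbidity timing in section 5.2 to patients for whom it can be met, or reword it.

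New users need not be made the main set: the primary objective covers treatment before, at and after index, and which stratum leads is the sponsor's choice.

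The cost is protocol wording, register extraction from July 2005, extra tables and smaller numbers per stratum. Section 9.2 expects 14,000–16,000 patients in all, but the size of each stratum is not known.

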3.2 Data collection method

This is an epidemiological registry study to evaluate clinical practice treatment in patients with BD. Data will be extracted from the National Patient Register (NPR) and merged with the National Prescribed Drug Register (PDR), and the Population Register. These data will also be matched with data on socioeconomic factors in order to describe the patients. The data will be obtained from various national registers in the LISA database maintained by Statistics Sweden (SCB).

Data will be collected for all patients who have been hospitalised in Sweden at least once since 1987 with a diagnosis during hospitalisation of BD and/or schizophrenia spectrum disorder.

All the registers include the Personal Identification Numbers (PIN) assigned to each resident in Sweden, enabling identification and linkage of records (Ludvigsson et al. 2009). The merging of the data from registers will be performed by National Board of Health and Welfare (Socialstyrelsen) who will replace the PIN of anonymous serial number before delivery of the database. No identification of patients will be possible elsewhere.

3.3 Data sources

3.3.1 National Patient Register

NPR includes all in-patient care in Sweden from 1987. From 2001 the register also contains information on outpatient visits at hospitals, including day surgery carried out by both private

Data base Audit Study Protocol DBA Code VD-NS-1101 Edition Number 1.0 Date

and public caregivers. Information on primary care visits or open care visit outside hospital are not included in the NPR. The information in NPR can be divided into four different groups

- 1. Patient data (personal registration number (PIN), sex, age, place of residence)
- 2. Geographic data (county council, hospital/clinic, department)
- 3. Administrative data (dates of admission and discharge, length of stay for inpatients, acute/planned admission, admitted from, discharged to) and
- 4. Medical data (the main diagnosis, secondary diagnoses, external cause of injury and poisoning, procedures and surgery).

Before 1997 the register contained a total of six diagnoses per admission, increasing to eight in 1997 and since 2009 an unlimited number of secondary diagnoses can be recorded.

At present, the NPR is updated once a year and normally available in September-October for the preceding year. The missing data on PIN for 2007 has been estimated to less than one percent.

3.3.2 Prescription Drug Register

The Prescribed Drug Register was started July 1, 2005 and is updated each month. The register comprises national coverage of dispensed drugs, pharmacies (dispensed drugs), not including OTC and in-patient care.

The variables include the patient's ID-number (PIN) and place of residence. Also registered is information about dispensed drugs (by ATC code), dates, dosages and for an unknown proportion indication in free text, DDDs, and expenditure. Information on the prescriber's profession (physician or other) and specialist code are registered.

PDR can be linked to other national registers by the unique patients PIN. Limitations include the lack of in-patient drug use and the lack of specific coding of the indication and prescribed dose. Information on indication and prescribed dose may in many cases be retrievable by text search procedures.

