4. SUBJECT POPULATION

The patient population will consist of all patients who have been hospitalised in Sweden at least once since 1987 with a diagnosis during hospitalisation of BD. Patients with a later diagnosis of schizophrenia spectrum disorder will be excluded.

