5.1.1 National Patient Register

- Date of admission and length of stay
- Main diagnosis
- Secondary diagnosis
- DRG codes set by the discharge hospital

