9. STATISTICAL METHODS AND SAMPLE SIZE DETERMINATION

9.1 Statistical evaluation – general aspects

A DBA is a study in which epidemiological methods including other methods that can be used to analyse human population health data.

The principal features of the planned statistical evaluation will involve descriptive statistics analysis the different populations.

The descriptive analysis (both for the primary and secondary objectives) will for the continuous variables be done by calculating mean, standard deviation, 95% CI, number of observations, minimum, maximum, median and number of missing observation and for categorical variables number of observations, frequencies and percentage.

Data base Audit Study Protocol DBA Code VD-NS-1101 Edition Number 1.0 Date

The analysed variables at the index date will be age, gender, educational level, marital status, living situation, occupation status, sick leave, income level, income source (salary/sick pension), country of birth, co-morbidities (as specified in section 5), co-medications (as specified in section 5).

The prescribers occupation, education and specialist code will be analysed, ownership (private/public) and country divided in quetiapine IR and quetiapine XR.

The variables analysed before the index date will be; number of hospital stays and sum of length of hospital stays.

The treatments after the index date will be analysed for the following variables: duration, dosage, drugs switches, DDD per package, number of prescribed packages for quetiapine IR/XR and co-medications including dosage and duration of these co-medications.

Attempts will be made to find the prescribed dose and the diagnosis from the free text on the prescription label on the drug for quetiapine IR and quetiapine XR either by text mining or by manually go through the different prescription labels.

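### Post-index duration, switches and refill-based dose take no account of in-patient days, although the hospital-stay data that would allow it are already extracted

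*Protocol*

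**What the plan says.** - **Objective.** Protocol section 2.1 makes treatment duration, dose, switches and add-on therapy the primary subject of the study.
- **Exposure source.** Drug use comes only from the Prescribed Drug Register (PDR). Section 3.3.2 says: "The register comprises national coverage of dispensed drugs, pharmacies (dispensed drugs), not including OTC and in-patient care". It also names the gap as a weakness: "Limitations include the lack of in-patient drug use and the lack of specific coding of the indication and prescribed dose". The same section adds that the prescribed dose can often be recovered by searching text.
- **Cohort.** Section 4 takes "all patients who have been hospitalised in Sweden at least once since 1987 with a diagnosis during hospitalisation of BD".
- **Index.** Section 3.1 sets index at the first dispensing of quetiapine in 2009-2010, or at 1 January 2009 for patients who started earlier.
- **Hospital data.** Among the NPR items in section 5.1.1 is "Date of admission and length of stay".
- **Analysis.** Section 9.1 gives hospital stays a place before index: "The variables analysed before the index date will be; number of hospital stays and sum of length of hospital stays". After index it says: "The treatments after the index date will be analysed for the following variables: duration, dosage, drugs switches", followed by package data and co-medications. Hospital days are not in the post-index list. Section 9.1 also plans an attempt to read the prescribed quetiapine dose from the label.
- **Time at risk.** Section 3.3.3 corrects person-time for emigration and death only.

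The protocol gives no gap rule, grace period or dose formula. No SAP was available.

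**The concern.** The protocol recognises that drugs given in hospital are invisible in its exposure source, and it obtains the data that locate those days. It then assigns these data to the pre-index period only, while the primary variables are measured mainly after index.

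During a stay the hospital supplies the drug. The supply at home lasts longer and the next pharmacy dispensing comes later. If duration or dose is derived from the interval between dispensings, the delay looks like a break in treatment or a lower daily dose. A start or a change of drug on the ward appears only at the first dispensing after discharge, and a change reversed before discharge is not seen at all.

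The error falls on primary variables and grows with the number of in-patient days, so it is not random noise. Patients admitted more often after index would appear less persistent and on lower doses than they were.

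**Working it through.** The protocol states no figure on this point, so there is nothing to reproduce. What follows illustrates direction and possible size. Pack size, stay length and admission rate are all assumptions.

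**1. One refill interval.** Let a pack last T days, let the patient spend h days in hospital with the home supply untouched, and let the refill come exactly at run-out. The interval is T + h, the apparent gap is h days, and the ratio of calculated to true dose is T/(T + h).
- T = 90, h = 7, 14, 28, 42: ratio 0.93, 0.87, 0.76, 0.68. For h = 28 this is 90/118 = 0.763.
- T = 30, same stays: 0.81, 0.68, 0.52, 0.42. For h = 28 this is 30/58 = 0.517.

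**2. One patient over a year.** The ratio is (365 - h)/365.
- h = 14, 28, 60, 90: 0.96, 0.92, 0.84, 0.75. For h = 28 this is 337/365 = 0.923.

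**3. Cohort mean.** If a share p is admitted after index for h days each, the mean dose bias over a year is -p × h/365.
- p = 0.05, h = 14: -0.2%.
- p = 0.10, h = 30: -0.8%.
- p = 0.30, h = 30: -2.5%.
- p = 0.50, h = 60: -8.2%.

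**4. False breaks.** A stay produces a false discontinuation only if the apparent gap exceeds the allowed gap g. With r admissions a year and exponential stays of mean m days, the one-year probability is 1 - exp(-r × exp(-g/m)).
- r = 0.5, m = 25: 24.0% at g = 15, 14.0% at g = 30, 4.4% at g = 60.
- r from 0.25 to 1, m from 15 to 25: 9-42% at g = 15 and 3-26% at g = 30.
- r = 0.05, m = 25: 2.7% at g = 15 and 1.5% at g = 30.

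**5. Effect of bridging.** Removing the h in-patient days from the interval returns the dose ratio to T/T = 1.00 and the apparent gap to 0, under the same assumptions.

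**6. How far bridging can run.** Section 3.3.1 says the NPR is updated yearly and is normally available in September-October for the preceding year. Section 7.1 places data collection in Q4 2011. NPR coverage therefore ends with 2010, as does the index window in section 3.1. A patient indexed on 1 December 2010 has at most 31 days in which stays can be seen.

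**The case against.** **Derivation rules belong in a SAP.** Section 9.1 lists variables and does not say how they are derived, and silence on bridging is not a decision to ignore stays. This stands in part: a missing gap rule is no fault in a protocol. But section 9.1 does state where hospital stays are used, and section 3.3.3 does state what corrects person-time. Neither includes in-patient days after index.

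**Dose may come from the label.** A reader might infer that the calculated dose will certainly be too low. The documents do not support that, because a dose read from label text is unaffected by hospital days. The protocol promises this only as an attempt, and only for quetiapine. Duration has no such alternative.

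**The cohort criterion is weak evidence.** A reader might infer that a cohort selected on hospitalisation spends much time in hospital during follow-up. One admission at any time since 1987 does not show this, since it may lie decades before index. The higher percentages in step 4 of the working rest wholly on assumed rates.

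**No comparison of outcomes is planned.** A reader might also infer a false difference between XR and IR. Section 1.2 rules out an outcome analysis between formulations. The severity difference reported in section 1.1 comes from schizophrenia inpatients. A bias that differs by formulation would require different in-patient time in the two groups, which the protocol does not show.

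**Bridging has its own weakness.** It assumes that quetiapine continued on the ward, which the PDR cannot confirm, and it could hide real stops or switches in hospital. Nor does it recover the date of a ward start. This stands, and is why bridging should accompany the unbridged analysis and not replace it.

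**Conclusion.** The point holds in conditional form. A limitation that the protocol itself discloses is not carried into the post-index analysis, although the data to address it are extracted. In-patient days after index may create apparent gaps, date ward starts and switches late, and understate any dose derived from refill intervals.

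The size in this cohort cannot be computed from the documents. The mean dose bias could be under 1% or several percent. It is large for an individual with a long stay. These figures assume untouched home supply, refill at run-out and a refill-based derivation. The documents do not establish that false gaps or low doses are certain, that they are common, or that they differ between XR and IR.

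**What to change.** Amend section 9.1 as follows.

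- Use NPR admission date and length of stay after index. Derive duration and refill-based dose with in-patient days bridged: they extend the current supply and are removed from the dose denominator. Stop at the end of NPR coverage.
- Present the bridged and unbridged results side by side as a sensitivity pair.
- Still record a change of drug at the first dispensing after discharge as a switch, so that bridging does not erase it.
- Report post-index in-patient days by formulation. This shows whether the issue is material and whether it differs between XR and IR.
- Report the share of index dispensings that fall shortly after a discharge, with the window fixed in advance. This does not recover ward starts but shows how common they may be.

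No new data are needed. The cost is some programming, an assumption about treatment on the ward that cannot be tested, and short bridged follow-up for patients indexed late in 2010.
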